 - Mild: Transient or intermittent episodes of unformed stools OR increase of ≤3 stools over baseline per 24-hour period
 - Moderate: persistent episodes of unformed to watery stools OR increase of 4-6 stools over baseline per 24-hour period
 - Severe: Bloody diarrhea OR increase of ≥7 stools per 24-hour period OR IV fluid replacement indicated

- Potentially Life Threatening: Life-threatening consequences (e.g. hypotensive shock)
- Nausea
 - Mild: Transient (<24 hours) or intermittent nausea with no or minimal interference with oral intake
 - Moderate: Persistent nausea resulting in decreased oral intake for 24-48 hours
 - Severe: Persistent nausea resulting in minimal oral intake for >48 hours OR aggressive rehydration indicated (intravenous fluids)
 - Potentially Life Threatening: Life-threatening consequences (e.g. hypotensive shock)
- Vomiting
 - Mild: Transient or intermittent vomiting with no or minimal interference with oral intake
 - Moderate: Frequent episodes of vomiting with no or mild dehydration
 - Severe: Persistent vomiting resulting in orthostatic hypotension OR aggressive rehydration indicated (intravenous fluids)
 - Potentially Life Threatening: Life-threatening consequences (e.g. hypotensive shock)

Long-term

The following long-term AEs and relevant details will be solicited:

- Gastrointestinal disorders
 - Inflammatory bowel disease
 - Irritable bowel syndrome
 - Celiac disease
 - Colon cancer
- Chronic infectious diseases (no therapy, outpatient, inpatient, ICU care)
- Autoimmune diseases
 - Inflammatory arthritis
 - Thyroid disease
 - Connective tissue diseases
 - Idiopathic thromobocytopenic purpura
- Metabolic disease
 - Diabetes Type 2 (diet controlled, oral hypoglycemic, insulin, uncontrolled/complication associated)
 - Metabolic syndrome (including obesity independently)
 - Non-alcoholic fatty liver disease
- Neuro-psychiatric disease
 - Multiple sclerosis
 - Depression/Anxiety
- Cardiovascular disease
 - Myocardial infarction (NSTEMI/STEMI)

- Stroke
- Cardiovascular related death

VI-C. Monitoring of Adverse Events

Each subject will be monitored for the occurrence of AEs, including SAEs. Each subject will be followed for safety monitoring at each follow-up interval.

- Subjects will be questioned at each follow-up interval regarding stool
 patterns, abdominal pain, fevers, and subjective well-being. First, subjects
 will be questioned about the possible occurrence of adverse events in a
 generalized way, such as, "How have you been feeling since your last
 visit?" Subsequent solicited questions and relevant details will be asked if
 there is a positive response. Site Investigators will be contacted by study
 representative if there is a suspected or reported AE
- Subjects having AEs will be monitored with relevant clinical assessments and laboratory tests, as determined by the site Investigator
- AEs, actions taken as a result of AEs, and follow-up results will be recorded as well as in the subject's source documentation. Follow-up laboratory results should be filed with the subject's source documentation
- Subjects will receive a follow-up phone call 6 and 12 months post-FMT to record any SAEs, new medical conditions/new medications, or changes in pre-existing medical conditions

VI-D. Assessment of Adverse Events

1. Assessment of Severity

The severity of AEs will be assessed according to the following definitions: •Mild: the AE is noticeable to the patient and/or the Investigator, but does not interfere with routine activity

•Moderate: the AE interferes with routine activity, but responds to symptomatic therapy or rest

•Severe: the AE significantly limits the patient's ability to perform routine activities despite symptomatic therapy

2. Assessment of Causality

The Investigator must assess the relationship of any AE (including SAEs) to FMT, as related or not related, based on clinical judgment and using all available information, and may include consideration of the following factors:

• Possible alternative causes of the AE, including the disease under treatment, pre-existing conditions, concomitant use of other drugs, and presence of environmental or genetic factors

- The temporal association between FMT exposure and onset of the AE
- Whether the manifestations of the AE are consistent with known actions or theoretical toxicity of FMT

The causal relationship between FMT and the AE will be assessed using one of the following categories:

Not Related: An AE is not associated with FMT if:

• Temporal relationship is lacking (e.g., the event did not occur within a reasonable time frame following administration of FMT); or

• Other causative factors more likely explain the event (e.g. pre-existing condition, other concomitant treatments);

Related: An AE is attributed to FMT if:

• There is a positive temporal relationship (e.g. the event occurred within a reasonable time frame following FMT); and

• The AE is more likely explained by FMT than by another cause

VI-E. Reporting Safety Observations by the Investigator to the Sponsor

1. Reporting of Non-serious AEs

All AEs, regardless of seriousness, severity, or causal relationship to FMT, will be recorded in the AE section of the subject case report form.

2. Reporting of FMT Exposure during Pregnancy

If a female subject or the female partner of a male subject becomes pregnant during the course of study, the Investigator must report this occurrence to the Sponsor within **72 hours** of becoming aware of the pregnancy. The Investigator is required to follow up on the pregnancy until it has completed. The outcome of the pregnancy and the status of the newborn (if applicable) will be reported within 24 hours of becoming aware. If the female partner of a male subject becomes pregnant, the Investigator must obtain consent to collect pregnancy information (including the status of the newborn, if applicable).

3. Reporting of Safety Observations by the Investigator

Any occurrence of the following events or outcomes must be reported expeditiously by the Investigator or qualified designee to the local IRB and to the Sponsor, who will be responsible for reporting the event to the FDA:

- 1. SAE related to FMT material
- 2. Death of a subject related to FMT material

The site Investigator is to report any safety observations from the list above to the Sponsor within **72 hours** of becoming aware of the event, who in turn, will notify the FDA. Any observation that is also an AE will be recorded on the subjects case report form along with any actions taken. If not all information is available at the time of initial report, follow up SAE reports will be completed and submitted.

Any occurrence of the following events or outcomes must be reported by the Investigator or qualified designee to the local IRB and to the Sponsor, who will be responsible for reporting the event to the FDA:

- 1. SAE unrelated to FMT material
- 2. Death of subject unrelated to FMT material
- 3. Hospitalization related to CDI
- 4. New or worsening medical condition, or new medications

The Investigator is to report any safety observations from the list above to the Sponsor within **7 days** of becoming aware of the event. The Sponsor will notify the FDA in its Annual Report. Any observation that is also an AE will be recorded on the subjects case report form along with any actions taken. If not all information is available at the time of initial report, follow up SAE reports will be completed and submitted.

The site Investigator is required to follow SAEs until resolution, regardless of whether the subjects are still participating in the study. Resolution is defined as:

- Resolved with or without residual effects
- Return to baseline for a pre-existing condition
- Fatal outcome; if autopsy is performed, the autopsy report must be provided to the Sponsor.

VI-F. Monitoring the study database and submitting safety reports

The Sponsor will notify FDA of any unexpected fatal or life-threatening suspected adverse reaction related to FMT material as soon as possible, but no later than 7 calendar days after the Sponsor's initial receipt of the information. The Sponsor will notify the FDA and all participating Investigators in an IND safety report of potentially serious risks from this study as soon as possible, but no later than 15 calendar days after the Sponsor receives the safety information and determines that the information qualifies for reporting. Participating Investigators include all Investigators enrolling subjects under the Sponsor's IND. In addition, the Sponsor will identify in each IND safety report, all IND safety reports previously submitted to FDA concerning a similar suspected adverse reaction and will analyze the significance of the suspected adverse reaction in light of previous, similar reports or any other relevant information. The Sponsor will evaluate a suspected adverse reaction in the context of other related reports or adverse events. The Sponsor will periodically review and analyze the entire safety database, for IND safety reporting purposes, and also to update Investigator brochures with new safety information. An IND safety report will be submitted when any of the following criteria are met:

A. Serious and unexpected suspected adverse reaction related to FMT material

A serious and unexpected adverse reaction is a SAE as determined by the Investigator or Sponsor, as defined previously, in combination with unexpected, defined as not being listed in the Investigator Brochure. At the request of the FDA, it will also include any documented infectious disease, defined as a new onset infection in the recipient after FMT and the infection present in the safety aliquot, which is a sample of the exact specimen that was transferred to the patient.

B. Findings from other sources

The Sponsor will also expeditiously report any findings from clinical, epidemiological, or pooled analysis of multiple studies or any findings that

suggest a significant risk in humans exposed to FMT and thought related to the material.

C. Increased occurrence of serious suspected adverse reactions related to FMT material

The Sponsor will report any clinically important increase in the rate of a serious suspected adverse reaction over that listed in the protocol.

VI-G. Halting Rules

Specific safety findings will result in temporarily suspending enrollment until a safety review is convened, the objective of which is to determine whether the study should continue per protocol, proceed with caution, be further investigated, be discontinued, or be modified and then proceed. Suspension of enrollment, for a particular group, such as colonoscopy group, or for the entire study, is another potential outcome of a safety review.

Subsequent review of serious, unexpected, and related AEs by the Data and Safety Monitoring Board (DSMB), IRB, the Sponsor, or the FDA or relevant local regulatory authorities may also result in suspension of further trial interventions/administration of FMT at a site. The FDA and study Sponsor(s) retain the authority to suspend additional enrollment and study interventions/administration of FMT for the entire study, as applicable.

Findings that will trigger a safety review are

- Death related to FMT material
- Confirmed transmission of a clinically concerning infection from donor to subject via FMT
- If one or more subjects experiences a serious, unexpected adverse event related to FMT material
- Significant increase in frequency of events theoretically related to FMT material (specifically, new diagnoses of inflammatory bowel disease). Discussion on threshold will be discussed with DSMB and will be on a disease specific basis.

For individual subjects enrolled in the study: any subject who has an SAE related to FMT will be ineligible for a second FMT during the course of the study.

FDA/CBER will be notified by phone or fax within 48 hours if the study is halted for review.

VII. Minimizing Risks to Human Subjects

VII-A. Human Subjects Involvement, Characteristics and Design

1. IRB approval for stool donor program has been obtained; Local site IRB approval from *each* study center will be obtained subsequent to required FDA approval of IND.

2. Subjects will be given informed consent using the standard consent process for colonoscopy/enema. Additional theoretical risk for transmission of infectious agents, and other diseases and conditions will also be discussed.

3. Donors will be given informed consent and will tested for most common infectious agents. Individuals with communicable disorders or a history of high-risk behaviors will not be permitted to donate.

4. Protections against risk are provided in detail below.

A sample size of 150 patients will be recruited. These patients will have been treated at or referred to one of the study centers for management of recurrent CDI.

Additional sites may be asked to join this study as needed to expeditiously achieve the targeted enrollment. The initial study sites will include:

1. Brown University and Women's Medicine Collaborative Providence, Rhode Island

2. Indiana University Health University Hospital Indianapolis, Indiana

3. University of Virginia Health Systems Charlottesville, Virginia

4. Edward Hospital Naperville, Illinois

This will be an open-label, longitudinal cohort study with follow-up at Day 3, Week 6, Month 6 and Month 12. The estimated duration of this study is 24 months. No patient will be excluded from recruitment on the basis of ethnicity, race, or disability. Subjects are expected to range in age from 18-75. Subjects will all be outpatients and will likely have comorbidities. All subjects will be fully informed about the purposes of the study, and risks and benefits of the study, and informed consent for all phases of the study will be obtained. Patients who agree to participate will be free to withdraw from the project at any time.

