6. PROTOCOL

I. Study Overview and Specific Aims

The proposed multi-center, open-label, longitudinal cohort study aims to capture the safety profile of FMT in recurrent CDI, as well as to contribute additional efficacy data to the existing body of evidence. The proposed study includes collaboration with Investigators who are able to define the microbial landscape of patients pre- and post-FMT, and further elucidate if there is a microbial signature that predisposes patients to respond, fail treatment, or have adverse events from FMT.

Study Title

Safety of fecal microbiota **T**ransplantation: **O**penBiome **O**utcomes and **L**ongitudinal follow-up (STOOL) for recurrent *Clostridium difficile* infection

Specific aims (SA)

SA1. Determine the short-term (<6 weeks) safety of FMT for the prevention of further CDI recurrence.

Hypothesis: Careful donor screening for both infectious and non-infectious yet potentially microbiome-associated conditions minimize the risk of donor to recipient transmission of disease. Therefore, FMT will not be associated with meaningful number of *related* serious adverse events, recognizing that the recurrent CDI patient population is conventionally elderly with multiple comorbidities and may be at risk for FMT procedure-related complications compared to otherwise young and healthy individuals based on conventional literature.

SA2. Determine the long-term (6-12 months) safety of FMT for the prevention of further CDI recurrence.

Hypothesis: Careful donor screening for both infectious and non-infectious yet potentially microbiome-associated conditions minimize the risk of donor to recipient transmission of disease. Therefore, FMT will not be associated with meaningful number of *related* serious adverse events, recognizing that the recurrent CDI patient population is conventionally elderly with multiple comorbidities and may be at risk for developing new conditions, new medications or adverse events including death, but unrelated to FMT material.

SA3. Determine the longitudinal robustness of FMT clinical cure rate for the prevention of further CDI recurrence.

Hypothesis: We predict a clinical cure rate in keeping with the current literature (80-90%) at the12 month follow-up time interval. This predicted longitudinal response rate would exclude patients who require further antibiotics that put them at risk for CDI reinfection, not true recurrence.

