SA4. Collect pre- and post-FMT stool samples from patients with recurrent CDI as well as donor stools for microbiome analysis.

Hypothesis: Prior to FMT, recurrent CDI patients will have deficiencies of certain normal colonic flora.²² After FMT, these microbial populations will be restored, resulting in a durable transition to a diverse, stable community that resembles the composition of the healthy stool donor. We expect that this transformation will be stable in the absence of challenge with antimicrobial therapy.

II. Subject Inclusion/Exclusion Criteria

Definitions

- **Clostridium difficile infection**: At least 3 unformed stools over 24 hours for 2 consecutive days and either positive stool test (ELISA or PCR) for *Clostridium difficile* toxins or pseudomembranes on colonoscopy (SHEA-IDSA guidelines).²⁶
- **Clinical Cure**: Clinical resolution of diarrhea (<3 unformed stools for 2 consecutive days) with maintenance of resolution at 6-week follow-up period, at minimum, and no further need for antibiotic therapy for CDI. In keeping with SHEA-IDSA guidelines and an absence of 'test of cure,' subjects who meet aforementioned definition will be considered a clinical cure regardless of any incidental follow-up stool testing employed.²⁶
- **Clinical Non-Response:** Ongoing or development of diarrhea and the requirement for antibiotic therapy for CDI.

Inclusion criteria

- Adult (age 18-75 years old)
- Outpatient
- Third or further documented CDI episode and
- Unable to maintain CDI cure after standard therapy with oral vancomycin or fidaxomicin
 - Previous treatment with at least one course of tapered/pulse vancomycin or
 - Inability to taper or stop vancomycin or fidaxomicin without developing diarrhea requiring antibiotic therapy.
- Improvement of CDI symptoms on vancomycin or fidaxomicin

Exclusion criteria

[figure not shown]
- Unable to comply with study follow-up procedures at discretion of MD
- Unable to provide informed consent at discretion of MD
- Participating in another clinical trial
- Pregnant or nursing currently or planned pregnancy in next 1 year
- Evidence of toxic megacolon or gastrointestinal perforation
- Peripheral white blood cell count >30 x 10⁹/L and/or temperature >38 degrees Celsius
- Admission to an intensive care unit within prior 7 days for any reason
- Previously undergone FMT
- Severely immunocompromised patients

- HIV infection (any CD4 count)
- AIDS-defining diagnoses
- Inherited/primary immune disorder

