1. Colonoscopy/sigmoidoscopy: If patients experience clinical non-response and require vancomycin/fidaxomicin within 6 weeks post-FMT, after a 10 day course subject may opt to undergo a second FMT via colonoscopy with an alternate donor at the physician's discretion. Subjects will be followed per protocol for duration of study.

2. Enema: If patients experience clinical non-response and require vancomycin/fidaxomicin within 6 weeks post-FMT, after a 10 day course subject may opt to undergo a second FMT via colonoscopy with an alternate donor at the physician's. Subjects will be followed per protocol for duration of study.

Withdrawal

- 1. All reasons for study withdrawal will be reported.
- 2. Classification of withdrawal:
 - Post-enrollment but pre-FMT
 - Post-FMT but lost to follow-up at:
 - o Day 3
 - o Week 6
 - o Month 6
 - \circ Month 12
 - All reasonable efforts will be exhausted to contact subjects, and data analysis will be based on the last available assessment.
 - Adverse event or serious adverse event mediating withdrawal
 - Rescind informed consent
 - Procedure-related ineligible patients
 - Patients undergoing colonoscopy/sigmoidoscopy and discovered to be ineligible due to newly discovered exclusionary criteria (eg. in-situ colorectal cancer). FMT will not be performed as part of this study and no data will be collected.

V. Study Observations and Measurements

Study Endpoints

Safety Endpoints

Safety will be assessed by short and long-term safety summaries classified into:

- 1. Serious Adverse Events (SAE)
- 2. Adverse Events (AE)
- 3. New medical conditions
- 4. Changes in pre-existing medical conditions

Efficacy Endpoints

Efficacy will be captured through:

- 1. Clinical cure rate of first FMT at 6-week follow-up
 - Colonoscopy
 - Sigmoidoscopy
 - Enema

2. Clinical cure rate of second FMT at 6-week follow-up, in patients with clinical non-response

- Colonoscopy/sigmoidoscopy non-response: Alternate donor FMT by colonoscopy
- Enema non-response: Alternate donor FMT by colonoscopy

Microbiome Endpoints

Sequencing data targeting the composition of the gut microbiome will be used to assess whether there are consistent microbial signatures associated with clinical cure, clinical non-response, or safety endpoints.

Data Collection

Case Report Forms will be utilized to capture and collect data (Appendix 4):

1. Baseline Assessment (Day 0 - Clinical Assessment)

Section 1: Clinical Evaluation

- Study patient identifier
- Date

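### SA3 aims at 12-month durability of cure, but the supplied text defines no 12-month endpoint or denominator, and two stated rules would tend to overstate durability if applied to it

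*Combined protocol and SAP*

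**What the plan says.** All references are to the combined protocol and SAP, part 6 (Protocol), unless noted.

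- **Specific Aims, SA3.** The aim is the longitudinal robustness of cure. The hypothesis puts it at 80-90% at the 12-month follow-up and continues: "This predicted longitudinal response rate would exclude patients who require further antibiotics that put them at risk for CDI reinfection, not true recurrence".
- **Definitions.** Clinical cure is resolution of diarrhea "with maintenance of resolution at 6-week follow-up period, at minimum, and no further need for antibiotic therapy for CDI". Clinical non-response is "Ongoing or development of diarrhea and the requirement for antibiotic therapy for CDI", with no exception for subjects who had taken other antibiotics.
- **Study Endpoints, Efficacy.** Two are listed: "Clinical cure rate of first FMT at 6-week follow-up" and "Clinical cure rate of second FMT at 6-week follow-up, in patients with clinical non-response".
- **Withdrawal.** Under loss to follow-up at Day 3, Week 6, Month 6 or Month 12, the text says that "data analysis will be based on the last available assessment".
- **Data Analysis, Aims 1-3.** Cure rates are calculated by site and pooled, with 95% confidence intervals. No time point, denominator or rule for antibiotic use is given.
- **Data Collection.** CDI recurrence, additional treatments and new medications are recorded at Months 6 and 12.

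**The concern.** SA3 is the only aim on how long a cure lasts, and Data Analysis claims to cover it. Yet the supplied text does not say what counts as a 12-month cure or who is in the denominator. The only guidance on who counts is the SA3 exclusion and the last-assessment rule, and both tend to favour a higher rate.

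The exclusion depends on something that happens after FMT. The protocol itself expects exposed subjects to do worse: SA3 says that the antibiotics put them at risk of reinfection, and SA4 expects a stable microbiota only without antimicrobial challenge. No list of qualifying antibiotics, time window or test to separate reinfection from recurrence is given. The forms, as summarised, record recurrence without that distinction.

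Exposure and death are unlikely to be negligible. The SA2 hypothesis says that these patients "may be at risk for developing new conditions, new medications or adverse events including death, but unrelated to FMT material", although it gives no rate for antibiotics or for death.

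In an open-label, single-arm study, an undefined denominator could be settled after the data are seen. A reader could also take an antibiotic-excluded rate for the rate in everyone treated.

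**Working it through.** **Figures in the plan.** The 80-90% is a prediction attributed to the literature, and n = 150 was chosen for feasible recruitment, so there is no calculation to reproduce. For scale, the exact (Clopper-Pearson) 95% interval at n = 150 is 72.7-86.1% for 120/150 and 84.0-94.3% for 135/150.

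The documents give no rates of antibiotic use, loss or late recurrence. Every rate below is an assumption.

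**1. Dropping exposed subjects.** Let a be the share exposed to antibiotics, and r0 and r1 the 12-month failure rates without and with exposure.

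- All treated: 1 − [a·r1 + (1 − a)·r0]
- Exposed dropped: 1 − r0
- Difference: a·(r1 − r0)

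With r0 = 15%, a = 10-40% and r1 = 15-40%:

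| a | r1 | All treated | Exposed dropped | Difference (points) |
|---|---|---|---|---|
| any | 15% | 85.0% | 85.0% | 0 |
| 10% | 30% | 83.5% | 85.0% | 1.5 |
| 20% | 30% | 82.0% | 85.0% | 3.0 |
| 30% | 40% | 77.5% | 85.0% | 7.5 |
| 40% | 40% | 75.0% | 85.0% | 10.0 |

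In counts for the third row: 120 unexposed × 0.15 = 18 failures and 30 exposed × 0.30 = 9 failures. All treated is (150 − 27)/150 = 123/150 = 82.0%; exposed dropped is (120 − 18)/120 = 102/120 = 85.0%. The 95% half-width at 82.0% is 1.96 × √(0.82 × 0.18/150) = 6.1 points, so a 3-point shift lies within sampling error. Unlike sampling error, it does not shrink with more subjects.

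**2. Carrying the last assessment forward.** Let c6 be the Week-6 cure rate, L the late recurrence among Week-6 cures, and d the share of those cures lost before any recurrence is seen. Assume that L is the same in lost and retained subjects.

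- True 12-month cure: c6·(1 − L)
- Carried forward: c6·[1 − L·(1 − d)]
- Difference: c6·L·d

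With c6 = 85%:

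- L = 5%, d = 10%: 80.75% true, 81.2% reported; 0.85 × 0.05 × 0.10 = 0.4 points
- L = 10%, d = 20%: 76.5% true, 78.2% reported; 0.85 × 0.10 × 0.20 = 1.7 points
- L = 15%, d = 30%: 72.25% true, 76.1% reported; 0.85 × 0.15 × 0.30 = 3.8 points

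Counting all lost subjects as failures instead of cures changes the rate by c6·d, which is 8.5 to 25.5 points over the same range. That is an outer bound, reached only if every lost subject recurred.

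**3. Both together.** Take Week-6 failure of 10%, and late recurrence of 5% without and 25% with antibiotics. With a = 20% and d = 10%, the true all-treated rate is 0.9 × (0.8 × 0.95 + 0.2 × 0.75) = 81.9%; the reported rate is 0.9 × (1 − 0.05 × 0.9) = 85.95%. With a = 30% and d = 20%, the rates are 80.1% and 86.4%.

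**The case against.** The strongest reply is that neither rule is tied to a 12-month analysis. The exclusion describes a predicted rate inside a hypothesis and is not repeated in Data Analysis. The last-assessment sentence is a general rule under Withdrawal. That stands, and it is why the overstatement is stated only as a tendency if the rules are applied.

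A rate free of antibiotic challenge is also a legitimate target, and SA4 suggests that it is deliberate. This stands too. It argues for defining that rate and showing it beside the all-treated one.

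The text also offers more than silence. Cure is held to 6 weeks at minimum, the General Investigational Plan monitors clinical resolution to 12 months, and recurrence is collected then. A natural 12-month definition can be inferred, but it is not written down. Part of the gap may come from the supplied file: Section III, Design Methodology, has a heading but no content, and Appendices 4 and 5 are not shown.

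The consequence is limited. Safety is the main objective, the analysis is descriptive, and nothing is tested against 80-90%.

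A reader might infer that the exclusion removes only exposed subjects whose CDI returns, so that only failures leave the denominator. In the example above that would give 123/141 = 87.2%, or 5.2 points more. SA3's wording does not favour this: it excludes patients who require such antibiotics, most naturally all of them.

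**Conclusion.** The concern holds as a gap in specification with a likely direction. In the supplied text, SA3 has no 12-month endpoint, denominator or antibiotic rule, and both stated rules tend to raise the rate if applied to it. Under the assumed ranges, the exclusion adds 0 to 10 points (nothing if exposed subjects fail no more often) and carry-forward adds about 0.4 to 3.8 points. The true size cannot be taken from the documents.

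Two stronger conclusions are not supported. A reader might infer that the plan commits to an inflated 12-month rate, but Data Analysis contains no such exclusion. A reader might also take the bound with all lost subjects counted as failures for the bias itself, but nothing suggests that all of them recur. The change should be made, with medium confidence, for an aim that is secondary to safety.

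**What to change.** Add one endpoint to Efficacy Endpoints and Data Analysis: sustained clinical cure of the first FMT through Month 12 in all FMT-treated subjects. Any CDI recurrence or clinical non-response after the first FMT counts as failure, whatever antibiotics were taken.

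- Report the antibiotic-excluded rate beside it, labelled as such. Fix the exclusion rule, the qualifying antibiotics and the time window before analysis.
- For this endpoint, do not carry a Week-6 cure forward. Keep all treated subjects in the denominator, state how many were lost or died without recurrence, and show bounds with them counted as failures and as cures.
- Report cures after a second FMT separately.

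The cost is wording in SA3, Efficacy Endpoints, Data Analysis and Withdrawal, plus a little more analysis. Recurrence and new medications are already collected at Months 6 and 12, so the proportion and its bounds need no new data. The downside is a possibly lower headline 12-month rate.
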